9. STATISTICAL CONSIDERATIONS

The data will be analyzed by the Sponsor and/or designated contract research organization. Any data analysis carried out independently by the Investigator should be submitted to the Sponsor before publication or presentation.

When appropriate, data will be summarized by dose cohort and regimen within each part.

9.1 STATISTICAL HYPOTHESES

Not applicable

9.2 SAMPLE SIZE DETERMINATION

This study is intended to obtain preliminary safety, PK, PD, and activity information in the treated populations, and the sample sizes do not reflect explicit power and Type I error considerations.

The maximum planned enrollment for this study is approximately 270-280 participants for both Parts A and B.

For the dose escalation stage in Part A, up to DLT evaluable participants are planned for the Q2W schedule with an additional participants if confirmation of safety, PK, RO and/or biomarkers are needed prior to opening Part B cohorts. The exact sample size cannot be pre-determined and depends on the number of cohorts needed to reach the MTD/RDE with the maximum planned dose set at 2.1 g.

Up to approximately participants may be enrolled in the expansion stages across the indication-specific cohorts in Part B.

9.3 POPULATIONS FOR ANALYSES

For purposes of analysis, the following populations are defined in Table 7.

Table 7 Analysis Populations

Population	Description
Dose Limiting Toxicity	The DLT-evaluable population is defined as all participants who received at least two doses of study medication and either:
	experienced a DLT within the DLT period OR
	cleared the DLT period without a DLT
	The DLT period is 21 (Q2W) from Day 1/Cycle 1 to Day 7/Cycle 2. If there is a delay in Cycle 2 treatment the DLT period should be adjusted to cover Day 7/Cycle 2 up to a maximum of 35 (Q2W) days, since the maximum dose delay allowed is 14 days.
Efficacy	All participants in the safety population who received at least one dose of study drug and who have at least one baseline and one on-study tumor assessment. Participants who received at least one dose of study drug and discontinued the study because of progression before the first on-study tumor assessment will be considered as response-evaluable.
Safety	All participants who received at least one dose of the study treatment, whether prematurely withdrawn from the study or not, will be included in the safety analysis. Unless otherwise specified, the safety population will be the default analysis set used for all analyses.
Pharmacokinetic	All participants who have received at least one dose of study treatment and who have data from at least one post-dose sample will be included in the PK analysis population. Participants will be excluded from the PK analysis population if they significantly violate the inclusion or exclusion criteria, deviate significantly from the protocol, or if data are unavailable or incomplete which may influence the PK analysis. Excluded cases will be documented together with the reason for exclusion. All decisions on exclusions from the analysis will be made prior to database closure.

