4.1.1 Length of the Study

The duration of the study for each participant will be up to 27 months (Parts A and B), divided as follows:

- Screening: Days 28 to 1
- Treatment Period: Cycle 1 Day 1 to Month 24 (may be modified if supported by emerging data).
- Safety follow-up: 60 (\pm 7) days after last treatment with RO7121661 for Part A; 90 (\pm 7) days after last treatment with RO7121661 for Part B.
- Survival follow-up: 90 (\pm 7) days after last treatment with RO7121661; then every 3 months (\pm 2 weeks) for total 24-month period after initial dose.

The treatment period may be prolonged past month 24 if the participant is still benefitting from treatment at the time of the last visit at the end of the two-year period. Participants may extend treatment within the ongoing study whether they are on treatment or are on a treatment pause at the 24-month time point. During the extended treatment period, the participant follows the SoA as indicated for "Subsequent Cycles." Participants will be treated until disease progression, unacceptable toxicities, or

withdrawal of consent. For participants who extend their treatment, the safety follow-up will be performed 60 (\pm 7) days for Part A or 90 (\pm 7) days for Part B after the last treatment with RO7121661 and survival follow-up every 3 months (\pm 2 weeks) thereafter for a total of 48 months after initial dose, or end of the study.

4.1.2 Dose-Escalation Decision Criteria

For Part A, RO7121661 dose-escalation will be carried out according to a mCRM with EWOC design and will be based on the occurrence of DLTs. The dose-toxicity relationship is described by a 2-parameter logistic regression model, where the probability of DLT is expressed as a function of dose. The model is continuously updated as additional participant information becomes available (for further information see Appendix 10).

A minimum of participants per cohort will be enrolled and treated in a sequential manner with one week between the first and second participant and at least 2 days between subsequent participants. However, if the first participant experiences a DLT within the first week, then the time between the treatment of subsequent participants within the same cohort may be increased.

A new cohort can be opened when at least participants per cohort are considered DLT evaluable, i.e., if they received 2 doses and either:

- experienced a DLT within the DLT period
- cleared the DLT period without a DLT

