The DLT period is 21 days from Day 1/Cycle 1 to Day 7/Cycle 2. If there is a delay in Cycle 2 treatment the DLT period should be adjusted to cover Day 7/Cycle 2 up to a maximum of 35 days, since the maximum dose delay allowed is 14 days.

Once at least participants per cohort are DLT-evaluable, the logistic regression model will be updated with the treatment outcome (i.e., the occurrence of DLT). Thus, a new estimate of the MTD (defined as the dose with the highest probability that the DLT rate is within the target of 20-35% and a relatively low probability <25% that the DLT rate is above 35%) will be derived. In addition, the model will recommend a dose for the new cohort of participants, with the EWOC recommendation being either the new estimate of the MTD or the highest allowable dose based on pre-specified safety constraints (e.g., maximum increments), whichever is lower.

Built in safety constraints are in place to prevent exposing participants to undue risk of toxicity. For instance, in the absence of DLT, the maximum allowable dose-increment will be 200% (i.e., next dose could be as high as 3-fold the previous dose) for dose-levels <700 mg and 100% (i.e. 2-fold) for dose-levels \ge 700 mg. In addition, in case of one event meeting DLT criteria in a dose-level, the maximum allowable dose

increment becomes 100% (i.e. 2-fold); while in the presence of 2 DLTs an increment of 50% is allowed (i.e. 1.5-fold). For further information see Table 1 in Appendix 10.

The dose escalation decision and selection of the dose for the next cohort, guided by the mCRM EWOC recommendation, will also take into account an overall review of safety and available PK and/or PD data as well as any additional data. Subject to clinical judgment, and upon agreement between the Sponsor and the Investigators on the next dose-escalation step, the new cohort can then be opened for enrollment.

The design will continue as described, until one of the pre-defined stopping criteria is satisfied (see Section 4.1.4), or the RDE has been defined, whichever comes first.

4.1.3 **Dose Limiting Toxicities**

For the purpose of this study, a DLT will be defined as any of the following events attributed to RO7121661 (i.e., related to RO7121661) and occurring during the DLT window:

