A DLT is defined as a clinically significant AE (classified according to the National Cancer Institute Common Terminology Criteria for Adverse Events [NCI CTCAE] v.5.0, as applicable) or significant laboratory abnormality: 1) occurring during the DLT assessment period of 21 days from the start of the first RO7121661 administration; 2) considered to be related to study treatment RO7121661 by the Investigator and; 3) is not attributed to disease progression or another clearly identifiable cause.

Investigators are encouraged to perform additional tests to determine the underlying etiology and most appropriate attribution.

For the purpose of this study the following AEs are considered DLTs:

- Hematological toxicities:
 - Grade 4 neutropenia (ANC $< 0.5 \times 10^9$ /L) lasting > 5 days.
 - Grade ≥ 3 febrile neutropenia associated with single body temperature > 38.3°C or sustained body temperature ≥ 38°C for > 1 hour, and/or with infection.
 - Grade 4 thrombocytopenia lasting>48 hours.
 - Grade 3 thrombocytopenia associated with bleeding episodes requiring a platelet transfusion.
 - Grade 4 anemia
 - Grade ≥ 3 anemia with hemolysis
- Any non-hematological toxicity of Grade ≥ 3 including:
 - Any Grade 3 immune-mediated AE.
 - Grade 3 hyperbilirubinemia lasting for > 48 hours or Grade 4 hyperbilirubinemia.

- Grade≥3 AST or ALT elevations with hyperbilirubinemia of Grade≥2.
- Grade 4 AST or ALT elevations.
- Grade ≥ 3 nausea, vomiting, or diarrhea despite maximal supportive treatment.
- Grade ≥ 3 non-hematological laboratory abnormality requiring medical treatment/intervention or hospitalization.
- The following Grade ≥ 3 non-hematological toxicity are exceptions for consideration as DLTs:
 - Alopecia (any grade).
 - Grade 3 nausea or vomiting that resolves to Grade ≤ 1 with or without supportive therapy within one week.
 - Grade 3 hypophosphatemia resolved within one week.
 - Grade ≥3 fatigue/asthenia that resolves to Grade ≤2 within one week.
 - Grade 3 anorexia or constipation.

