Failure to recover from any RO7121661-related toxicity that results in a dose-delay of the next scheduled administration of more than 14 days is defined as a DLT.

4.1.4 **Stopping Rules Criteria**

Part A Dose Escalation 4.1.4.1

The algorithm of the mCRM with EWOC will propose to stop the dose escalation under the following circumstances:

- The maximum sample size of evaluable participants has been reached **OR**
- Enough information on MTD has been achieved (i.e., at least a minimum of participants enrolled and at least participants have been accrued near the MTD dose - where near is defined as differing from the MTD by at most 15% - and the probability that the MTD dose lies within the target toxicity interval is above 50%)

OR

The maximum dose has been tested and is considered safe (i.e., at least a minimum of participants have been accrued at the maximum dose or near differing from the maximum dose by at most 5% - and it is at least 50% likely that the probability of a DLT for that maximum dose is below 20%).

Due to the exploratory nature of this clinical study, any part of its conduct can be discontinued at any time at the discretion of the Sponsor. This will not constitute a premature termination of the study. The Sponsor will notify the Investigators and Health Authorities if the study is discontinued or the development program is terminated.

4.1.5 **Communication Strategy**

For Part A: Upon completion of all screening evaluations and confirmation that a participant has met all inclusion and exclusion criteria, investigator sites will contact the Sponsor to confirm the dose, participant number and cohort assignment via a Confirmation of Enrollment form (ESF). This will guarantee that the Sponsor is notified

prior to the administration of RO7121661 to any participant. Then sites will need to contact the interactive response technology system (IRT) vendor who will generate confirmation of participant number, dose and cohort assignment. The IRT participant number should be generated prior to first dose.

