6.6 DOSAGE MODIFICATION

Instructions for RO7121661 administration, change of infusion rate, and interruption of infusion are provided in Section 6.1 and Section 7.

Participants who experience toxicities fulfilling the definition of a DLT in the first cycle, or DLT-equivalent toxicities in subsequent cycles should be discontinued from study treatment. Nevertheless, the Investigators, after discussion with the Sponsor, will have the option to reduce the dose of RO7121661 to the previous tolerated dose level, if participant is deemed to be deriving clinical benefit.

A delay of RO7121661 administration for up to two cycles, will be acceptable to allow for resolution of toxicity to NCI CTCAE Grade ≤ 2 for hematological toxicities or Grade ≤ 1 for non-hematological toxicities (with the exception of a toxicity considered as non-RO7121661 related).

If the toxicity does not resolve to NCI CTCAE Grade ≤ 2 for hematological toxicities or ≤ 1 for non-hematological toxicities and the participant is unable to resume treatment with RO7121661 after this time (omission of two doses), no additional doses will be administered and the participant will be withdrawn from study treatment, unless the participant exhibits a clinical benefit and this is discussed by the Investigator and the Medical Monitor. It should be noted that infusions/cycles not occurring at the anticipated schedule, are considered as delayed, not missed.

Further dose-reductions may be implemented once safety and toxicity data from the dose-escalation have been evaluated.

For participants with documented liver metastasis and elevated liver function test (LFT) results at baseline, further elevations of LFT results may not require dose interruptions if there are no progressive changes in the ALT and/or AST (less than a doubling) and if there are no progressive elevations in total bilirubin or international normalized ratio (INR).

Investigators are encouraged to contact the Sponsor for further guidance if needed. After Cycle 1 is completed, dose modifications should be discussed with the Sponsor. In these instances, a confirmation with the Sponsor is requested and documentation in the eCRF is requested. Treatment delays of up to 3 days due to logistical considerations (e.g., center closure for holiday) are generally acceptable and do not need to be discussed with the Sponsor. In no instance are cycles shorter than 14 days of duration (i.e. Q2W) allowed in this study.

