PFS will be defined as the time from study treatment initiation (Cycle 1 Day 1) to the first occurrence of documented disease progression (based on RECIST Version 1.1 Investigator's assessment) or death from any cause, whichever occurs first. For

participants who do not have documented progressive disease or death during the study, PFS will be censored at the day of the last tumor assessment.

Sensitivity analyses of response endpoints (ORR, DRC, DoR, and PFS) may include the evaluation of response according to iRECIST.

OS is defined as the time from the first dose of study treatment to the time of death from any cause. Participants who are still alive at the time of analysis will be censored at the time of their last study assessment (for active participants) or at the last date known alive (for participants in follow-up).

9.4.3 Safety Analyses

Unless otherwise specified all safety analyses listed in Table 9 will be based on the safety population. All safety parameters will be analyzed using descriptive statistics, summarized and presented in tables. Data will be summarized by dose and regimen (if applicable) within each part.

Safety will be assessed through summaries of DLTs (for Part A), adverse events, changes in laboratory test results, changes in vital signs and ECGs, and exposure to study treatment.

Table 9 Safety Statistical Analysis Methods

Endpoint	Statistical Analysis Methods
AEs	The original terms recorded on the eCRF by the Investigator for AEs will be coded by the Sponsor.
	For classification purposes, preferred terms will be assigned by the Sponsor to the original terms entered on the eCRF, using the most up-to-date version of the MedDRA terminology for AEs and diseases. AEs will be graded according to NCI CTCAE grades v5.0.
	Adverse events will be summarized by mapped term and appropriate thesaurus level. Toxicity grade, seriousness, and relationship to study treatment will be presented, as well as summaries of deaths, AEs leading to death and premature withdrawal from study treatment. Glossary of AEs, medication, and procedures will be provided.
Nature and frequency of DLTs	DLT events will be presented by individual listings. The MTD will be estimated with a mCRM–EWOC using DLT-evaluable participants. The MTD estimate will be presented along with 90% Credible Intervals.

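### DLT-evaluable requires two doses even after a DLT, so a DLT before dose 2 that ends treatment drops out of the mCRM-EWOC estimates

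*Combined protocol and SAP*

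**What the plan says.** The evaluability rule appears twice. Table 7 in Section 9.3 has "The DLT-evaluable population is defined as all participants who received at least two doses of study medication and either", followed by two alternatives: a DLT within the DLT period, or the period cleared without one. Section 4.1.2, which governs the opening of a new cohort and the model update, has "DLT evaluable, i.e., if they received 2 doses and either" and the same two alternatives.

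The definition of a DLT in Section 4.1.3 has no dose-count condition; the event is one "occurring during the DLT assessment period of 21 days from the start of the first RO7121661 administration". The same section adds that failure to recover from a related toxicity, resulting in "a dose-delay of the next scheduled administration of more than 14 days is defined as a DLT".

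Section 6.6 says what follows a DLT: "Participants who experience toxicities fulfilling the definition of a DLT in the first cycle, or DLT-equivalent toxicities in subsequent cycles should be discontinued". This means stopping the study drug. Dose reduction is left as an option where the participant appears to benefit.

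Table 9 (Section 9.4.3) says the MTD is estimated with the mCRM-EWOC "using DLT-evaluable participants. The MTD estimate will be presented along with 90% Credible Intervals". Appendix 10 likewise has the model use data from evaluable patients.

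**The concern.** The two-dose condition stands before the either/or, so it applies to both branches. With 14-day cycles, the first 14 of the 21 window days pass before dose 2 is due. A participant with a DLT in those days who follows the Section 6.6 default receives one dose only. That participant has a DLT by Section 4.1.3 but is not DLT-evaluable by Table 7. The same is true of a DLT defined by a prolonged delay of dose 2 when dose 2 is never given. No other section makes a one-dose DLT evaluable.

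Selection into the analysis set then depends on the outcome: participants who clear the window enter, and some who had an early DLT do not. The quantities affected are the posterior DLT rate, the EWOC overdose probability, the model-based stopping rules, and the reported MTD with its 90% credible interval. All would make a dose appear safer than it is. The mock runs in Appendix 10 Table 1 show a different behaviour, because there an observed DLT always enters the model and sharply limits the next step (for example 615 mg with no DLT and 220 mg with one, starting from 210 mg).

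**Working it through.** **Inputs.** All are from Appendix 10 and Section 4.1.2 unless marked as assumed.
- Model: logit p(d) = α + β·ln(d/70).
- Prior: bivariate normal, mean (−1.736, 0.326), variances 0.8948 and 0.0747, covariance 0.1859.
- Target interval 20–35%; overdose constraint P(p > 0.35) < 0.25.
- Mock-run cohort size 3. The cohort minimum in the body text is redacted.
- Step cap: 3-fold below 700 mg without a DLT, and 2-fold "in case of one event meeting DLT criteria in a dose-level".

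The posterior was computed by grid integration. The next dose maximises P(0.20 ≤ p ≤ 0.35) subject to the overdose constraint and the cap.

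**Step 1: reproduce Appendix 10 Table 1.** From 210 mg after a clean 70 mg cohort, the rerun gives 630 mg with no DLT (table: 615) and 220 mg with one (table: 220). From 70 mg with one DLT it gives 85 mg (table: 80). Ten of the 16 cells match within 3% or 2 units. In the other cells the tabulated dose has a target probability within 0.0021 of the maximum, so the differences reflect a flat criterion.

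**Step 2: one DLT among 3 treated, earlier cohorts clean.** Counted, the cohort contributes 1/3. Excluded under Table 7, it contributes 0/2. The cap after one DLT refers to the event rather than to evaluability, so the highest permitted next dose is twice the current one: 2 × 70 = 140, 2 × 210 = 420, 2 × 615 = 1230 mg.

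| Current dose | Next dose | P(p > 0.35), counted 1/3 | excluded 0/2 | Crosses 0.25? |
|---|---|---|---|---|
| 70 mg | 140 mg (2-fold cap) | 0.282 | 0.114 | yes |
| 210 mg | 420 mg (2-fold cap) | 0.276 | 0.102 | yes |
| 615 mg | 1230 mg (2-fold cap) | 0.234 | 0.075 | no |
| 70 mg | 210 mg (mock-run step) | 0.356 | 0.158 | yes |
| 210 mg | 615 mg (mock-run step) | 0.334 | 0.133 | yes |
| 615 mg | 1840 mg (mock-run step) | 0.284 | 0.097 | yes |

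The last three rows are the no-DLT steps of Table 1. They show what the model alone would report; the 2-fold cap would not permit them. If a further DLT-free participant is added (0/3), the excluded values at those doses are 0.124, 0.101 and 0.071, so the gap widens.

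**Step 3: the reported Part A DLT at 1.2 g.** Its timing relative to dose 2 is not given. Assumed: 3 participants each at 70, 210 and 600 mg without a DLT, and 3 at 1200 mg.
- P(p > 0.35) at 2.1 g before any 2.1 g data: 0.141 counted, 0.036 excluded.
- After 6 DLT-free participants at 2.1 g: 0.014 and 0.002. P(p < 0.20) is 0.864 and 0.964.
- With 6 assumed at 1200 mg, the overdose probabilities are 0.056 and 0.012 before 2.1 g data, and 0.005 and 0.001 after.

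Every overdose value is under 25%, and the 50% threshold of the maximum-dose stopping rule is passed either way.

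**Step 4: general size.** Let p be the true DLT rate and f the share of DLTs that stop treatment before dose 2. Among N treated, Npf are excluded, so the apparent rate is Np(1 − f) / N(1 − pf) = p(1 − f)/(1 − pf).

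| True p | f = 1/3 | f = 1/2 | f = 2/3 |
|---|---|---|---|
| 20% | 14.3% | 11.1% | 7.7% |
| 35% | 26.4% | 21.2% | 15.2% |

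The documents do not give f, so these are illustrative values. At f = 0 there is no bias.

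**The case against.** The wording looks more like a drafting slip than a chosen exclusion. Section 7.1 lists replacement when the DLT period is not completed for reasons unrelated to the drug, and Section 7.2 says safety withdrawals are not replaced. On the literal rule an early-DLT participant would neither count nor be replaced, which is hard to operate. The sponsor may well have counted such participants in practice. That stands as a statement of probable intent, but no section says it, and a data set programmed from Table 7 would leave them out.

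The largest differences in Step 2 arise at steps the 2-fold cap forbids. That is correct, and the capped rows are the relevant ones; two of the three still cross the bound. It is also true that 0/2 may not reach the redacted cohort minimum and so may trigger no update, but adding a participant makes the discrepancy larger.

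Escalation is over, the RDE is the maximum dose of 2.1 g, no MTD was identified, and Section 4.4 also rests the choice on tolerability, PK and product limits. The event remains in the DLT listings, the safety population and the sponsor–investigator review. All of this stands and limits the practical effect to the reported model estimates.

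**Conclusion.** The point holds. As written, the definition removes DLTs from the model according to outcome, in the direction that makes a dose look safer, and it conflicts with Sections 4.1.3 and 6.6. One dropped DLT in a cohort of 3 can move the overdose probability across the plan's own 25% bound at the lower doses, even with the 2-fold cap (140 and 420 mg), though not at 1230 mg.

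For Part A as reported, the effect is unknown and probably small. It depends on whether the 1.2 g DLT preceded dose 2 and on cohort sizes that had to be assumed, and no decision changes in any of the runs. What remains exposed is the MTD estimate and its 90% credible interval. The point should be fixed, but it does not show that the RDE is wrong.

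**What to change.** In Section 4.1.2 and Table 7, define DLT-evaluable as either (a) at least one dose and a DLT within the DLT period, or (b) two doses and the DLT period cleared without a DLT. Confirm that the final mCRM-EWOC estimate includes every Part A participant who meets (a), in particular the 1.2 g DLT, and rerun the model if it does not.

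Separately, reconcile the windows. Section 4.1.3 fixes 21 days, while Section 4.1.2 and Table 7 extend the period "up to a maximum of 35 days, since the maximum dose delay allowed is 14 days" (21 + 14 = 35). A DLT defined by a delay of more than 14 days cannot be established until after Day 29 (15 + 14). That lies outside the fixed 21 days but can fall within 35.

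The cost is a short wording change in two places and at most one rerun of the existing model. The MTD estimate and its interval may become less favourable.
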